### 2.1.1 DEVICE NAME AND INDICATIONS FOR USE

The Renuvion APR Handpiece is a sterile, single use electrosurgical (monopolar) device intended to be used in conjunction with compatible generators for the percutaneous delivery of radiofrequency energy and/or helium plasma for cutting, coagulation and ablation of soft tissue. The compatible Generators operate at an adjustable power of up to 40W (expressed as 0-100% where 100% is 40W) and provide an adjustable helium gas flow of 1-5 LPM.

Radiofrequency energy is delivered to the handpiece by the generator and used to energize the electrode. When helium gas is passed over the energized electrode, a helium plasma is generated for soft tissue cutting, coagulation

or ablation. The Renuvion APR system consists of a handpiece (Figure 1), an electrosurgical unit (ESU, Figure 2), and a supply of helium gas (Figure 2). RF energy is delivered to the handpiece by the ESU and used to energize an electrode. When helium gas is passed over the energized electrode, a helium plasma is generated which allows for conduction of the RF energy from the electrode to the subject in the form of a precise helium plasma beam.

[figure not shown]

FIGURE 1: RENUVION APR HANDPIECE

[figure not shown]

FIGURE 2: ELECTROSURGICAL UNIT AND HELIUM TANK

The Apyx Medical Corporation Renuvion/J-Plasma helium plasma family of products has received FDA clearance under 510(k) numbers K090586, K112233, K142975, K151325, K152570, K170188, K170777, K183610, K191484, K191542, K192867, K202880 for the cutting, coagulation, and ablation of soft tissue.

## 2.1.2 PRECLINICAL STUDIES

### Pre-Clinical Studies to Support Safe Tissue Temperatures during Device Use

During the use of the Renuvion system in open surgical procedures involving subdermal tissue coagulation, the tip of the Renuvion handpiece is placed in the subcutaneous tissue plane through the same access ports used during suction assisted lipolysis procedures (liposuction). In this use, it is important to establish that both the external epidermal tissue temperatures and the internal subdermal tissue temperatures remain within safe limits. The following pre-clinical studies were conducted to measure these temperatures on both live porcine skin tissue and ex vivo human skin tissue:

#### 1. RP-18032301: Evaluation of Porcine Skin Tissue Epidermal Temperature During Subdermal J-Plasma (Renuvion) Application (Non-GLP)

This was a pre-clinical study in which the Renuvion system was used to coagulate the subdermal tissue of porcine skin at various treatment parameters in order to measure the maximum temperature on the surface of the epidermis. In this study, the maximum recorded epidermal surface temperatures were 39.1°C and 40.2°C. These temperatures were recorded after performing six consecutive passes of the Renuvion system under the same area of tissue. Six consecutive passes under the same tissue was included in the study to represent a “worst case” scenario. Six passes are not commonly performed clinically. However, even in this “worst case” scenario the epidermal surface temperature remained within safe limits. Pedroso, et.al, reported that because of superficial thermal safety concerns, the skin surface temperature should be maintained below 45°C. This study was subsequently published. The summary of the published study is as follows:

*J-Plasma helium was used in porcine, liver, kidney and muscle tissue at 20%, 50% and 100% power and 1 L/min and 3 L/min gas flow at 1, 5, and 10 second intervals. J-Plasma was then used in ovarian and uterine tissue at maximum power and gas flow settings in intervals of 1, 5, 10 and 30 seconds. Concluded that J-Plasma has predictable thermal spread in a variety of tissue types. Thermal depth of spread increased linearly with increased power setting, gas flow rate, and exposure time. Even at settings that greatly exceeded the manufacturer's recommendation, the depth of thermal spread associated with the J-Plasma device was less than 3 mm (regardless of the type of tissue) and the diameter of lateral spread was 12 mm or less.*

#### 2. RP-18040201: A Study Evaluating Tissue Contraction, External Tissue Temperature, and Internal Tissue Temperature When Using J-Plasma (Renuvion) on Ex Vivo Abdominoplasty Tissue (non-GLP)

This was a pre-clinical study that was performed on ex vivo human tissue collected by a surgeon during previously conducted abdominoplasty procedures. The Renuvion system was used to coagulate the subdermal tissue of the human skin samples at various treatment parameters. During treatment, both the maximum external epidermal tissue temperatures and the maximum internal subdermal tissue temperatures were measured and recorded. The maximum external tissue temperatures ranged from 24.9°C to 37.8°C. This data serves to validate the maximum external tissue temperatures of 39.1°C and 40.2°C reported in RP-18032301 measured in a live porcine model. The maximum internal tissue temperatures ranged from 40°C to 80°C. It is known from the literature that the reported range of temperatures causing collagen shrinkage varies from 60°C to 80°C. Therefore, in order to cause soft tissue coagulation and collagen contraction, the target internal tissue temperature should be within this range. Both the external and internal temperatures remained within safe limits when using the Renuvion system to coagulate the subdermal tissue of human skin samples.

The results of the above summarized pre-clinical testing support the safe and effective use of the Renuvion® system in dermatological and general surgical procedures involving subdermal tissue coagulation.

## 2.2 POTENTIAL RISKS AND BENEFITS

### 2.2.1 POTENTIAL RISKS

This treatment modality was designed to inherently minimize the risk to the subject. However, treatment with energy-based modalities (laser, radiofrequency, and plasma devices) produce subsequent heating of the soft tissue that could involve the following commonly Expected Treatment Effects (ETEs): discomfort/pain, edema, erythema, ecchymosis, hypoesthesia, temporary sensory nerve injury (touch sensitivity, itching, temporary numbness/tingling), transient migratory firmness, and temporary and/or transient crepitus.

In addition to commonly expected treatment effects, treatment with the Renuvion APR device could involve the following risks: helium embolism into the surgical site due to inadvertent introduction into the venous or arterial blood supply system, unintended burns (deep or superficial), pneumothorax, pneumomediastinum, temporary or permanent motor nerve injury, ischemia, fibrosis, infection, gas buildup, bleeding, hematoma, seroma, subcutaneous induration, pigmentation changes, increased healing time, unsatisfactory scarring, asymmetry and/or unacceptable cosmetic result.

Risks associated with tumescent anesthesia (lidocaine and epinephrine) include blurred vision, mental/mood changes, drowsiness, dizziness, unusually slow heartbeat, rash, itching, swelling, anxiety, apprehensiveness, restlessness, tremor, weakness, sweating, palpitations, pallor, nausea and vomiting, headache, and respiratory difficulties.

Subjects using drugs that reduce coagulation (aspirin or NSAIDs) may experience increased bruising or bleeding at the treatment site. Any other medications prescribed for the procedure or after-procedure by the investigator have their own risks; these risks should be discussed with the subject.

A grounding pad is used to ground/neutralize the electrical current. Subjects undergoing radiofrequency treatment will be kept away from contact with metal parts which are grounded, or which have appreciable capacitance to earth.

As the Investigator will be treating the subjects per their Standard Practice of Care, there may be additional risks associated with the gynecomastia procedure. The Investigator will be responsible for properly reviewing all potential risks with the patient prior to treatment.

Any unexpected or unforeseen complications will be managed by the investigator throughout the conduct of the study. Unforeseen or unexpected side effects not listed above will be reported to the sponsor and regulatory representatives (IRB) as they occur.

#### 2.2.1.1 *MINIMIZATION OF POTENTIAL RISKS*

These risks are mitigated by utilizing qualified clinical Investigators who have training and are experienced in gynecomastia procedures and Renuvion procedures. In addition, risks are mitigated by including only those subjects that meet the study eligibility criteria.

### 2.2.2 POTENTIAL BENEFITS

This study is being conducted to determine if there is a possible benefit of using the Renuvion APR device as an adjunct procedure to Gynecomastia surgery.

### **3. STUDY PURPOSE**

The purpose of this pilot study is to assess the safety and effectiveness of the Renuvion APR device, when used as an adjunct procedure in gynecomastia surgery. This study may provide data to support a future pivotal study.

### **4. STUDY DESIGN AND ENDPOINTS**

#### **4.1 DESCRIPTION OF THE STUDY DESIGN**

This study is a prospective, multi-center, single-blinded, randomized pilot clinical trial to be conducted at up to 3 clinical site(s). Up to 10 subjects will be enrolled and treated if they meet the inclusion/exclusion criteria and provide written informed consent. A higher number of subjects than 10 may be enrolled due to screen failures or withdrawal of consent.

Subjects meeting all entrance criteria and confirmed eligible will be enrolled. The gynecomastia surgery and Renuvion APR System will be used as per the Investigator's standard clinical practice. During the procedure, fat transfer and treatment of the lateral chest and/or axilla is not allowed. Subjects will only be treated on one side utilizing the Renuvion APR System. Images will be taken prior to treatment and during each follow-up visit. These images will be assessed for correct identification of the Renuvion-treated side by blinded Independent Photographic Reviewers (IPRs) following the D180 visit. Baseline assessments and pre-treatment images should be obtained within the 30 days prior to study treatment. Endermology is not allowed post-procedure. Post-procedure compression will be used for 2-3 weeks with a standard compression vest for all subjects.

Following study participation, the subject will be offered an optional balancing treatment to the side not previously treated with Renuvion.

#### **4.2 DURATION OF STUDY**

Recruitment for this study is estimated to take 6 months. Following the treatment visit, subjects will be followed for a total duration of 180-days. Therefore, the anticipated total duration of the study is approximately 12 months.

#### **4.3 STUDY ENDPOINTS**

##### **4.3.1 PRIMARY SAFETY ENDPOINT**

The primary safety endpoint is the bilateral occurrence of adverse events.

##### **4.3.2 ADDITIONAL ENDPOINTS**

Other additional endpoints for this study are as follows:

1. Bilateral analysis of change to STPTUP (Tebbetts & Adams High 5 Measurements) from baseline to day 30, 90, and 180.
2. Bilateral analysis of change to STPTIMF (Tebbetts & Adams High 5 Measurements) from baseline to day 30, 90, and 180.
3. Bilateral analysis of male chest measurements (Murphy) from baseline to day 30, 90, and 180.
4. Bilateral analysis of skin excised during the procedure by Gynecomastia Grade (Rohrich Classification).
5. Bilateral analysis of gland tissue removal methods (Longheu) during the procedure by Gynecomastia Grade.
6. The Principal Investigator, sub-investigator or qualified clinician delegated by the principal investigator, will complete a bilateral PGAIS assessing overall aesthetic improvement in the treatment area at day 30, 90, and 180 post-treatment.
7. The subject will complete a bilateral SGAIS assessing overall aesthetic improvement in the treatment area at day 30, 90, and 180 post-treatment.
8. The subject will complete a bilateral Patient Satisfaction Questionnaire (PSQ) at the 180-day follow-up visit.

9. Baseline images compared to Day 30, 90, and 180 images will be assessed for correct identification of Renuvion-treated side by blinded IPRs.

[figure not shown]
#### 4.3.3 EVALUATION TOOLS

The following evaluation tools will be used in this study:

##### 4.3.3.1 SOFT TISSUE PINCH THICKNESS OF THE UPPER POLE (STPTUP)

The STPTUP is a measure of the soft-tissue pinch thickness of the upper pole, by isolating skin and subcutaneous tissue superior to the breast parenchyma, pinching firmly, and measuring the thickness with a caliper. See **Figure 3**.

This will be performed at Baseline, Day 30, 90, and 180.

**FIGURE 3: STPTUP**

##### 4.3.3.2 SOFT TISSUE PINCH THICKNESS AT THE INFRAMAMMARY FOLD (STPTIMF)

The STPTIMF measures soft-tissue pinch thickness at the inframammary fold by isolating skin and subcutaneous tissue at the inframammary fold, pinching firmly, and measuring the thickness with a caliper. See **Figure 4**.

This will be performed at Baseline, Day 30, 90, and 180.

**FIGURE 4: STPTIMF**

##### 4.3.3.3 BILATERAL MALE CHEST MEASUREMENTS (MURPHY)

Measurements of the male chest will be taken for each patient prior to procedure and at days 30, 90 and 180 as indicated in **Table 2**.

TABLE 2: CHEST MEASUREMENTS (MURPHY)

Measurement	Description
A	Suprasternal notch to nipple
B	Internipple distance
C	Suprasternal notch to nipple plane
D	Midclavicular point to nipple
E	Nipple plane to umbilicus
F	Umbilicus to pubic symphysis
G	Coracoid process to nipple plane
H	Nipple plane to medial epicondyle
I	Coracoid process to medial epicondyle

#### 4.3.3.4 GYNECOMASTIA GRADE (ROHRICH CLASSIFICATION)

This classification of gynecomastia is based on the amount and character of breast hypertrophy and degree of ptosis. This will be performed at Baseline and all follow-up visits. See **Table 3**.

TABLE 3: ROHRICH CLASSIFICATION

Classification	Description
Grade I	
I A: Primarily glandular*	Minimal hypertrophy (<250g of breast tissue) without ptosis
I B: Primarily fibrous*	
Grade II	
I A: Primarily glandular*	Moderate hypertrophy (250-500g of breast tissue) without ptosis
I B: Primarily fibrous*	
Grade III	
Glandular or fibrous*	Severe hypertrophy (>500g of breast tissue) with grade I ptosis
Grade IV	
Glandular or fibrous*	Severe hypertrophy with grade I or III ptosis

\*Fatty and glandular tissue is determined by a pinch test medially, laterally, and beneath the nipple-areola complex

#### 4.3.3.5 MODIFIED GLOBAL AESTHETIC IMPROVEMENT SCALE (GAIS) (ADDITIONAL ENDPOINT)

The Modified Global Aesthetic Improvement Scale (GAIS) is a subjective rating of improvement in treatment results compared to pre-treatment. The Investigator will grade the overall improvement of the treatment area as indicated in **Table 4** by comparing the subject's appearance at follow-up visits against a photograph taken prior to procedure. Likewise, the subject will also rate their improvement compared to pre-treatment as shown in **Table 5**.

The modified GAIS results will be collected at the 30-day, 90-day and 180-day follow-up visits.

**TABLE 4: MODIFIED GLOBAL AESTHETIC IMPROVEMENT SCALE EVALUATION - INVESTIGATOR**

Rating	Description
Very much improved	Optimal cosmetic result from this procedure in this subject
Much improved	Marked improvement in appearance from the initial condition, but not completely optimal for this subject
Improved	Obvious improvement in appearance from the initial condition
No change	The appearance is essentially the same as the original condition
Worse	The appearance is worse than the original condition
Much worse	The appearance is much worse than the original condition
Very much worse	The appearance is very much worse than the original condition

**TABLE 5: MODIFIED GLOBAL AESTHETIC IMPROVEMENT SCALE EVALUATION - SUBJECT**

Rating	
Very much improved	
Much improved	
Improved	
No change	
Worse	
Much worse	
Very much worse	

The Global Aesthetic Improvement Scale (GAIS) is a 5-point scale that rates global aesthetic improvement from the pretreatment appearance. The ratings are worse, no change, improved, much improved, and very much improved. It was validated by [name], et al. for this use. In this study both live observation and photo review are utilized by the physician or a qualified, delegated clinician and subject in order to assign a score. The PGAIS must be performed by the principal investigator, sub-investigator or qualified clinician delegated by the principal investigator. Both the PGAIS and SGAIS should be completed in two steps:

- Based on a live assessment of the subject while referring to the subject's pre-treatment photographs (subjects should be given a hand mirror for assessment); and
- Based on a comparison of the subject's pre-treatment photographs to the current post-treatment photographs.

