## 7.2 STUDY PROCEDURE

The bilateral gynecomastia surgery and Renuvion APR System use will be as per investigator's standard clinical practice. During the procedure, fat transfer and treatment of the lateral chest and/or axilla is not allowed. The Renuvion APR System will be used on one side only, and alternate consecutively between patients, starting on the right side. For example, subject 001 will be treated with Renuvion on the right side, subject 002, will be treated on the left, subject 003 will be treated on the right, etc. This treatment scheme will continue until enrollment has completed at each site. The subjects will be blinded as to which side has been treated with Renuvion.

Procedure data and adverse events will be captured.

Endermology is not allowed post-procedure for the duration of the study.

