**TABLE 3: STUDY REQUIRED PROCEDURES**

	Baseline/ Pre-Procedure Screening 	Procedure (Day 0)	30 Days	90 Days	180 Days
			23-37 days	80-100 days	165-195 days
Informed Consent	X				
Assess Inclusion/Exclusion Criteria	X				
Medical History	X				
General Physical Exam	X				
Review Medications	X		X	X	X
Patient Treatment Survey	X				
Imaging (front, lateral, and oblique) 	X		X	X	X
Gynecomastia Grade	X		X	X	X
STPTUP	X	X	X	X	X
STPTIMF	X	X	X	X	X
Chest Measurements	X	X	X	X	X
Study Procedure		X			
Adverse Event Assessment		X	X	X	X
Modified Global Aesthetic Improvement Scale (GAIS) 			X	X	X
Subject Satisfaction Survey					X

 Pre-procedure Screening assessments to take place within 30 days prior to undergoing the procedure.

 To be completed by Investigator and study subject at day 30, day 90 and day 180 follow-up visits.

 Images used for IPR Assessment.

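### Site-rated side contrasts (PGAIS, pinch thickness, side-specific chest distances) carry a risk of observer bias of unknown size, and no blinded clinician grades improvement

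*Protocol*

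**What the plan says.** **Who is blinded.** Section 4.1 describes the study as single-blinded. Section 7.2 states "The subjects will be blinded as to which side has been treated with Renuvion", and Section 7.4 repeats it. The three photographic reviewers are blinded too (Sections 4.1 and 4.3.3.7). No one else is.

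**Who treats.** Section 2.2.1: "As the Investigator will be treating the subjects per their Standard Practice of Care, there may be additional risks associated with the gynecomastia procedure". Whoever operates therefore knows the device side.

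**Who grades PGAIS.** Section 4.3.3.5 opens with "The Investigator will grade the overall improvement of the treatment area", and the footnote to the schedule table in Section 7.3.2 reads "To be completed by Investigator and study subject at day 30, day 90 and day 180 follow-up visits". Neither mentions a delegate. The text below Table 5, like endpoint 6 in Section 4.3.2, is wider: "The PGAIS must be performed by the principal investigator, sub-investigator or qualified clinician delegated by the principal investigator". None of these places excludes the operator or asks for a rater unaware of side.

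**Who measures.** For pinch thickness, Section 4.3.3.2 gives the technique, "pinching firmly, and measuring the thickness with a caliper", and Section 4.3.3.1 is alike. Section 4.3.3.3 lists nine chest measurements. None of the three sections names a rater or mentions blinding.

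**How side is assigned.** Under Section 7.2 the device side alternates by subject number, with subject 001 on the right and 002 on the left.

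**What the blinded photographic review produces.** Under Section 4.3.3.7 each reviewer chooses the treated side. No grade of improvement is asked for.

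**The concern.** Each subject is his own control, which removes differences between subjects. It does not remove the expectation of a rater who scores both sides of one chest and knows which side had the device. That expectation enters the within-subject difference directly, and no later analysis can take it out.

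PGAIS is most exposed, because the protocol itself calls the scale subjective. Pinch thickness depends on how firmly the examiner pinches. Distances that differ by side, such as A (suprasternal notch to nipple) and D (midclavicular point to nipple), depend on how landmarks are found and the tape is laid.

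Section 3 gives effectiveness as part of the purpose and says the data may support a pivotal study. A side difference in these endpoints could be carried forward as a device effect when part of it came from the rater.

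**Working it through.** **Step 1: compare roles with knowledge of side.**

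| Endpoint | Rater in the protocol | Blind to side? |
|---|---|---|
| PGAIS by side | Investigator (4.3.3.5 opening, 7.3.2 footnote); or sub-investigator or delegate (4.3.2, 4.3.3.5 below Table 5) | Not required; the operator knows the side |
| STPTUP, STPTIMF | Not named | Not required |
| Chest distances | Not named | Not required |
| SGAIS, PSQ | Subject | Yes |
| Side identification | Three photographic reviewers | Yes |

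The first three rows have no safeguard. The last two are blinded, but they give the subject's view and a choice of side, not a clinician's grade.

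**Step 2: which chest measurements matter.** B (internipple distance) and F (umbilicus to pubic symphysis) give no side contrast, so they are outside this point.

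**Step 3: would a delegate be blind?** Not by being a delegate alone. Under the alternation in Section 7.2, anyone who knows the scheme and the subject number can work out the side.

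**Step 4: scale, by assumption only.** The protocol gives up to 10 treated subjects (Section 10.2) and descriptive statistics (Section 10.1). It gives no standard deviation, effect size or error rate, so there is no figure to reproduce.

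*Counts.* Suppose no true effect, no ties, and a probability q that the rater favours the device side. Then P(at least 8 of 10) = Σ C(10,k) q^k (1−q)^(10−k) for k = 8 to 10.

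- q = 0.5 (unaware of side): (45 + 10 + 1)/1024 = 0.055
- q = 0.6: 0.121 + 0.040 + 0.006 = 0.167
- q = 0.7: 0.233 + 0.121 + 0.028 = 0.383 (from unrounded terms)
- q = 0.8: 0.302 + 0.268 + 0.107 = 0.678 (from unrounded terms)

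*Means.* A constant rater shift in standard errors is shift / (SD/√10).

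- PGAIS, assumed paired SD of 1 category: SE = 1/√10 = 0.316. Shifts of 0.25, 0.5 and 1 category are 0.79, 1.58 and 3.16 standard errors.
- Pinch thickness, assumed shift of 1 mm: with a paired SD of 2 mm, 1/0.632 = 1.58; with 4 mm, 1/1.265 = 0.79.

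*As a false-positive rate.* For a paired t test at two-sided 5% with 10 pairs, take the noncentral t with 9 degrees of freedom and noncentrality b√10, where b is the shift in SDs of the paired difference. For b = 0.25, 0.5 and 1.0 the rate is 0.109, 0.293 and 0.803. The protocol plans no such test, so this shows scale only.

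**The case against.** The case against has weight. The protocol openly describes a single-blinded pilot. The primary endpoint is adverse events, and the measures in question are additional endpoints reported descriptively. The blinded subject rates each side on SGAIS at three visits and completes a side-specific PSQ at day 180, and three blinded reviewers examine the photographs. Nothing shows that any rater was or will be biased.

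That limits the point in four ways. A reader might infer any of the following, and the documents do not support them:

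- *That the effectiveness results could be investigator expectation alone.* That expectation could not by itself produce the SGAIS, PSQ or photographic findings.
- *That the operator takes the caliper and tape readings.* The protocol is silent on the rater; it permits this but does not say it.
- *That the protocol already authorises a delegated clinician for all these measures.* The express permission covers PGAIS only. For the others, a separate rater is neither named nor barred.
- *That a delegate absent from surgery would settle the matter.* The alternation can still reveal the side, and a site may have no uninvolved clinician.

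What survives is that no blinded clinician grade of improvement exists, and that the site-rated contrasts carry no label saying they are unblinded. Descriptive reporting does not help, because the same shift enters the reported means and counts.

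**Conclusion.** The concern holds in this limited form. The treating investigator, who knows the Renuvion side, may give the PGAIS grade for each side. Pinch thickness and the side-specific chest distances may be taken by a rater who knows it. These additional endpoints therefore carry a risk of observer bias. Its presence and size cannot be established from the protocol.

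The figures above rest on assumed leans, shifts and standard deviations. They show that with 10 subjects even a moderate lean could produce a lopsided side comparison, not that one will occur. For additional endpoints in a descriptive pilot this does not undermine the study. It is worth correcting because the reviewers and images needed for a blinded grade are already in place.

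**What to change.** 1. **Add a blinded grade.** In Sections 4.3.3.5 and 4.3.3.7, have the three photographic reviewers grade each side on Table 4 from the existing baseline and follow-up images. They should do so before choosing the treated side, so that the guess does not colour the grade, and without subject numbers or the allocation scheme. Report this as the blinded improvement comparison.
2. **Label the site ratings.** Report side contrasts in site PGAIS, pinch thickness and chest distances as unblinded. The exception is where they were taken by an available sub-investigator or delegated clinician who was not at the surgery and has no access to the operative record or the side allocation. For that exception to mean anything, the side must not be readable from the subject number, as Section 7.2 now allows.
3. **Reconcile the rater.** Align the opening of Section 4.3.3.5 and the schedule footnote in Section 7.3.2 with the wider permission in Section 4.3.2 and below Table 5. Name who takes the measurements in Sections 4.3.3.1 to 4.3.3.3.

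**Cost.** At most 3 reviewers × 10 subjects × 2 sides × 3 visits = 180 extra grades by readers already engaged, with no new visit or procedure. Two limits remain. Photographic grades omit the live-assessment step of PGAIS, and caliper and tape data stay unblinded at any site without an uninvolved clinician.
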